Appendix 10.7 EU (EEA countries) and UK-specific requirements

Synopsis, Section 3.1 Objectives, Section 3.1.1 Efficacy Objectives, Section 3.2 Endpoints, Section 10.3.9 Primary Efficacy Analysis; In the UK and countries within the EU (EEA countries):

- The primary endpoint in the blinded treatment period is the proportion of participants able to achieve platelet counts at or above 50,000/ μ L for at least 8 out of the last 12 weeks of the 24-week blinded treatment period in the absence of rescue therapy.
- The primary efficacy analysis is as follows: The primary analysis will compare the proportion of participants in the adult ITT population who achieve durable platelet response defined as platelet counts at or above 50,000/ μ L for ≥ 8 out of the 12 scheduled observations in the last 12 weeks of the 24-week blinded treatment period in the absence of rescue medication between rilzabrutinib and placebo with a Cochran-Mantel-Haenszel test using the two stratification factors at a 2-sided alpha level of 0.05. Participants who do not respond in the first 12 weeks and enter the open label period will be treated as non-responders in the primary analysis. Participants who discontinue the study due to a rilzabrutinib-related AE, lack of efficacy or receive rescue medication (including an increase in allowed concomitant ITP medications dose) will be considered as non-responders. Sensitivity analyses will be conducted on the primary analysis.
- In the blinded treatment period, the following is a key secondary objective: To evaluate the change from baseline in IBLS.

- In the blinded treatment period, the following is a key secondary efficacy endpoint (the last endpoint in the multiplicity control): Change from baseline in IBLS assessment at Week 25
- Key secondary efficacy analysis: Compare the change from baseline in IBLS assessment at Week 25

EU (EEA countries) only

Throughout the protocol, the allowed age range for pediatric participants is ≥ 10 to < 18 years, where permitted by local regulation.

Synopsis and Section 5.1, Inclusion criterion 1:

Participants will be male and female with primary ITP with duration of > 6 months in pediatric participants aged ≥ 10 to < 18 years (where allowed by local regulation) and duration of > 3 months in adults ≥ 18 years.

Synopsis and Section 5.1, Inclusion criterion 3:

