## Country-specific definition [countries within the EU (EEA countries) and UK]

To qualify for a durable responder (Definition 2, [Section 1.2.2.1](#)), a participant must have met ALL of the following criteria:

- Platelet counts  $\geq 50,000/\mu\text{L}$  for at least 8 out of the last 12 weeks [Week 14 (Day 92) to Week 25 (Day 169)] during the 24-week double-blind treatment period, and
- Not rescued after 8 weeks of treatment and before Week 25 (or last IMP intake, whichever earlier). A participant who is rescued during this period will be considered as a non-responder, and,
- Not discontinued before Week 25 due to related TEAE (per investigator's assessment) or lack of response. A participant who discontinues before Week 25 and the reason for discontinuation is treatment related AE or lack of response will be considered as a non-responder.

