3. Discontinuation of study intervention before Week 25 due to reasons other than the aforementioned: data during the double-blind on-treatment period will be included in the analysis. Post-treatment data will be considered to have had no platelet response (composite strategy).

Note: per protocol, the end of study visit is performed at 4-week post-dose follow up where participants will have their final assessment (weekly post-dose platelet assessment not required starting from amended protocol 03).

**Missing data** will be handled as followed,

For durable platelet response Definition 2 ([Section 1.2.2.1](#)), missing data will be handled as follows,

- Missing data due to Covid-19 (per eCRF) are assumed missing at random and will be imputed using the participant's median value of available weekly platelet counts (a minimum of 3 available weekly platelet counts required) during the last 12 weeks of double-blind on-treatment period.
- Otherwise, missing data will be considered as no response. That is, if no platelet measurement is available at a specific weekly visit, that week will be considered to have had no platelet response.

[Table 4](#) in [Section 3.2.3](#) outlines assumption of missing data and its handling for each type of analyses - main analyses ([Section 3.2.2](#)) and sensitivity analyses ([Section 3.2.3](#)) of the primary efficacy endpoint.

The n (%) of participants with missing data during the last 12 weeks of the 24-week double-blind period will be summarized as follows,

- Any missing weekly platelet counts.
  - Due to any reasons,
  - Due to Covid-19,
- Number of missing weekly platelet counts: 1 to 2, 3 to 4, >4,
  - Due to any reasons,
  - Due to Covid-19.

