**Table 4 - Missing Data Handling for Primary Efficacy Endpoint**

Definition	Analysis Type	Estimand	Alternatives to main analysis	Missing data Handling	Missing data Assumption
Definition 1 a	Main c (Section 3.2.2)	Primary estimand (Composite)		No imputation of missing data	Not applicable
	Sensitivity (Section 3.2.3.1.3)		Alternative handling of missing data	Tipping-point analysis: post-treatment data considered missing for Intercurrent Event #3	Missing not at random: Assuming various treatment difference for missing data
	Sensitivity (for completers) (Section 3.2.3.2)	Modified primary estimand	Alternative analysis population	No imputation of missing data	Missing completely at random: completers are representatives of non-completers
	Sensitivity (Section 3.2.3.3)		Alternative handling of missing data due to Covid-19	Missing data due to Covid-19 imputed with the median value of available platelet counts	Missing (due to Covid-19) at random: missing data not associated with outcome
Definition 2 b	Main c (Section 3.2.2)	Primary estimand (Composite)		1) Missing data due to Covid-19 imputed with the median value of available platelet counts, 2) No response otherwise	1) Missing (due to Covid-19) at random: missing data not associated with outcome; 2) Missing (not due to Covid-19) not at random: Missing data indicates lack of response
	Sensitivity (Section 3.2.3.1.1)		Alternative handling of missing data	Missing data considered as no response	Missing not at random: Missing data indicates lack of response
	Sensitivity (Section 3.2.3.1.2)		Alternative handling of missing data	On-treatment missing data handled using multiple imputation	Missing at random: on-treatment missing data not associated with outcome
	Sensitivity (Section 3.2.3.1.3)		Alternative handling of missing data	Tipping-point analysis: post-treatment data considered missing for Intercurrent Event #3	Missing not at random: Assuming various treatment differences for missing data

Definition	Analysis Type	Estimand	Alternatives to main analysis	Missing data Handling	Missing data Assumption
	Sensitivity (for completers) ( Section 3.2.3.2 )	Modified primary estimand	Alternative analysis population	No imputation of missing data	Missing completely at random: completers are representatives of non-completers

All efficacy analyses based on ITT, unless otherwise specified.

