### **3.2.3.3 Sensitivity Analyses – modified primary estimand – missing due to Covid-19 imputed with participant's median value (for Definition 1)**

Sensitivity analysis on the durable response Definition 1 will be carried out via the same primary estimand and the same analysis method as defined in the main analytical approach ([Section 3.2.2](#)), after the handling of missing data due to Covid-19. That is, missing data due to Covid-19 (per eCRF) will be imputed using the participant's median value of available weekly platelet counts (a minimum of 3 available weekly platelet counts required) during the last 12 weeks of double-blind on-treatment period.

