## 4 SAMPLE SIZE DETERMINATION

A sample size of approximately 194 (129 versus 65 adult participants in the rilzabrutinib versus placebo arms, respectively) will provide 95% power to detect a 20% difference in response rates as defined in the primary endpoint ([Section 1.2.2.1](#)) between the 2 arms (25% vs 5%, in the rilzabrutinib versus placebo arms, respectively), using the Fisher's Exact test with a 0.05 two-sided significance level.

The assumption of a 25% response rate in the rilzabrutinib group is based on the Phase 2 study PRN1008-010 Part A (DFI17124 Part A) (durable response [8 out of the last 12 weeks with platelet count at or above 50,000/ $\mu$ L in the absence of rescue medication]) and the 5% response rate is estimated based on the observed placebo response in previous randomized controlled trials of ITP medications ([11](#)). The participants who are not evaluable for primary efficacy due to dropout or missing data will be considered as non-responders.

The pediatric sample size of 30 participants (20 participants on rilzabrutinib and 10 on placebo) was determined based on clinical practice and is adequate to descriptively describe the safety and efficacy in pediatric participants. With a sample size of 20 pediatric participants on rilzabrutinib the maximum width of an exact 90% CI on response rate would be 40%.

Calculations were made based on 2-sample Exact test using SAS® 9.4.

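### In the EU/UK main analysis, filling Covid-missing weeks with the participant's own median credits those weeks at a 50% response level, while Definition 2 requires 8 of 12, so response rates are biased upward

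*SAP*

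**What the plan says.** SAP 3.2.1 defines a Definition 2 responder by counts of at least 50,000/µL "for at least 8 out of the last 12 weeks [Week 14 (Day 92) to Week 25 (Day 169"), with no rescue after the first 8 weeks and no discontinuation for a related adverse event or lack of response. Protocol Appendix 10.7 likewise sets the denominator at "out of the 12 scheduled observations in the last 12 weeks of the 24-week blinded treatment period".

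SAP 3.2.2 and Table 4 give the main-analysis handling of gaps as "1) Missing data due to Covid-19 imputed with the median value of available platelet counts, 2) No response otherwise". In the words of 3.2.2, the Covid-missing weeks are "imputed using the participant's median value of available weekly platelet counts (a minimum of 3 available weekly platelet counts required"), and that minimum is the only condition. For gaps with any other cause, "if no platelet measurement is available at a specific weekly visit, that week will be considered to have had no platelet response".

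Definition 1 has no imputation in its main analysis and requires at least 8 observed counts. A sensitivity analysis for it (SAP 3.2.3.3) borrows the same fill: "missing data due to Covid-19 (per eCRF) will be imputed using the participant's median value of available weekly platelet counts".

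**The concern.** The fill and the endpoint work at different levels. The endpoint asks for two-thirds of weeks. The fill decides all Covid-missing weeks at once, according to whether the participant's median is at or above 50,000/µL, and that depends on about half of the observed weeks. A participant observed at 55% to 65% response, who would be expected to fall short of 8 of 12, receives full credit for each Covid-missing week. A single deterministic value also ignores week-to-week variation and the uncertainty of the imputation.

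The SAP classifies the same records differently elsewhere. In Table 5 (tipping-point analysis), a record with fewer than 8 observed responding weeks and fewer than 5 observed non-responding weeks is undetermined. Records of 6/10, 4/7 and 2/3 are therefore undetermined there but responders in the main analysis.

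At stake is the headline EU/UK response rate. The more cautious treatments of missing weeks appear only as sensitivity analyses.

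**Working it through.** **Plan's own figure.** The plan gives no number for this rule. The nearest is the 95% power for 129 versus 65 adults at 25% versus 5% (Fisher's exact test, two-sided 0.05). Exact enumeration gives 96.4%, so it reproduces. It does not depend on the fill.

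**Which records qualify.** Let m be the observed weeks, k of them at or above 50,000/µL, and 12 − m the Covid-missing weeks, with no other gaps. If k > m/2, the median is at or above 50,000, so the counted total is k + (12 − m). This is at least 8 exactly when m − k ≤ 4.

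| Observed m | Covid-missing | Smallest majority k | Counted of 12 | Proportional 12k/m |
|---|---|---|---|---|
| 3 | 9 | 2 | 11 | 8.0 |
| 5 | 7 | 3 | 10 | 7.2 |
| 7 | 5 | 4 | 9 | 6.9 |
| 8 | 4 | 5 | 9 | 7.5 |
| 9 | 3 | 5 | 8 | 6.7 |
| 10 | 2 | 6 | 8 | 7.2 |
| 11 | 1 | 6 | 7 (not a responder) | 6.5 |

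A bare majority is enough for 2 to 9 Covid-missing weeks; with one, 7/11 is needed. In the 2/3 record the fraction is adequate, but the classification rests on three counts. With an even m of 4, 6 or 8, exactly half can be enough: counts of 20, 30, 80 and 120 (×10³) have median 55, so 2/4 becomes 10/12. The two-thirds standard of Definition 1 would need 6/8, 6/9, 7/10 and 8/11, where the median rule accepts 5/8, 5/9, 6/10 and 7/11.

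**Effect on the probability of response, independent weeks (assumption), weekly chance 60%.**
- Complete data: P(Bin(12, 0.6) ≥ 8) = 0.438
- 1 missing: P(Bin(11, 0.6) ≥ 7) = 0.533
- 2 missing: P(Bin(10, 0.6) ≥ 6) = 0.633
- 4 missing: P(Bin(8, 0.6) ≥ 5) = 0.594; adding half of P(Bin(8, 0.6) = 4) = 0.232 for tied medians gives 0.594 + 0.116 = 0.710

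At a 40% weekly chance the same steps give 5.7%, 9.9%, 16.6% and 29.0% (17.4% at 4 missing if ties count as below 50,000).

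**Correlated counts (assumption: log-normal, within-person log SD 0.5, lag-1 correlation 0.5).** With person median 50,000 and between-person log SD 0.4, the rate is 38% complete, 45% with 2 missing and 50% with 4. With median 30,000 and SD 0.6 it is 15.7%, 19.3% and 22.2%. With median 30,000 and SD 0.8 the base is about 22%, rising by about 3 and 6 points. The added amount is thus about 3 to 7 points with 2 missing and 6 to 12 with 4.

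**Arm level.** If 10% of the rilzabrutinib arm has 2 to 4 Covid-missing weeks (assumption), the rate moves by 0.10 × 3 = 0.3 to 0.10 × 12 = 1.2 points, or 129 × 0.003 = 0.4 to 129 × 0.012 = 1.5 participants.

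**The case against.** The strongest reply is that the effect is small and already visible. The planned difference is 20 points. Platelets are measured at local laboratories, weekly visits may be remote, and the Covid guidance provides for home nursing, so Covid-missing weeks may be few. SAP 3.2.2 tabulates them, and no-response, multiple-imputation, tipping-point and completer analyses are all planned. This stands as a limit on size. It does not make the main-analysis rule unbiased.

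A second reply is that counting Covid-missing weeks as no response is worse. This is correct: in the first correlated setting 38% falls to 26% with 2 missing and 11% with 4, so that rule should not replace the median fill.

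Three stronger readings are tempting but not supported.
- A reader might infer a conflict with the 12 scheduled observations in Protocol Appendix 10.7, or with the sample-size statement "The participants who are not evaluable for primary efficacy due to dropout or missing data will be considered as non-responders". The first fixes the denominator and says nothing about gaps. The second is a planning assumption about participants who cannot be evaluated, and one whose weeks are filled under a pre-specified rule can be. Protocol 10.3.14 and the Covid contingency text of Appendix 10.7 leave missing-data handling to the SAP.
- A reader might infer that every missing week is credited to anyone with a majority. Only Covid-missing weeks are filled, one missing week is not enough at 6/11, and the rescue and discontinuation rules still apply.
- A reader might infer that the rule manufactures a treatment effect. It is the same in both arms. Without a drug effect, both arms would pass the Week 13 assessment alike.

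**Conclusion.** The concern holds as a bias in a stated main-analysis rule: the fill switches at one-half while the endpoint sits at two-thirds, and response rates rise in every setting examined. Week 13 non-responders leave blinded treatment, and SAP 3.2.3.2 expects more dropout on placebo, so fillable weeks should lie mostly in the rilzabrutinib arm. The rule would then tend to inflate a real difference slightly, by the 0.3 to 1.2 points in the rilzabrutinib rate shown above. That range rests on the assumed 10% share, which the documents do not give, and on the assumed response levels and correlation. It should be corrected, but it is unlikely to decide the trial.

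**What to change.** In the Definition 2 main analysis, impute Covid-missing weeks with the missing-at-random multiple imputation of SAP 3.2.3.1.2, restricted to those weeks. All other missing weeks stay no response. Combine by Rubin's rule and move the median fill to a sensitivity analysis.

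Settle the method and its fallback before unblinding. SAP 3.2.3.1.2 runs the imputation only if no placebo data need imputing or at least 3 placebo completers qualify, and that condition should not choose the primary method once the arms are known.

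As the fallback, score participants with Covid-missing weeks by Definition 1's existing standard: at least two-thirds of at least 8 observed weeks. It is mostly conservative. With independent weeks at 60% it gives P(Bin(10, 0.6) ≥ 7) = 0.382 with 2 missing and P(Bin(8, 0.6) ≥ 6) = 0.315 with 4, against 0.438 complete. Counting the gaps as no response gives 0.167 and 0.017. With one missing week the two coincide, since both need 8 observed responses. Keep no response as the sensitivity analysis already planned.

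In 3.2.3.3, state that imputed weeks do not count toward the minimum of 8 non-missing counts; the text leaves this open.

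The cost is SAP wording and a small programming change, because the sample code in SAP 5.7.2 imputes every missing week from 2 to 25 in flagged participants. The EU/UK response rate may come out slightly lower.

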### **3.2.3 Sensitivity analysis**

Sensitivity analyses will be performed in adults to assess the impact of the missing data handling strategy as outlined in [Table 4](#).

**Table 4 - Missing Data Handling for Primary Efficacy Endpoint**

Definition	Analysis Type	Estimand	Alternatives to main analysis	Missing data Handling	Missing data Assumption
Definition 1 a	Main c (Section 3.2.2)	Primary estimand (Composite)		No imputation of missing data	Not applicable
	Sensitivity (Section 3.2.3.1.3)		Alternative handling of missing data	Tipping-point analysis: post-treatment data considered missing for Intercurrent Event #3	Missing not at random: Assuming various treatment difference for missing data
	Sensitivity (for completers) (Section 3.2.3.2)	Modified primary estimand	Alternative analysis population	No imputation of missing data	Missing completely at random: completers are representatives of non-completers
	Sensitivity (Section 3.2.3.3)		Alternative handling of missing data due to Covid-19	Missing data due to Covid-19 imputed with the median value of available platelet counts	Missing (due to Covid-19) at random: missing data not associated with outcome
Definition 2 b	Main c (Section 3.2.2)	Primary estimand (Composite)		1) Missing data due to Covid-19 imputed with the median value of available platelet counts, 2) No response otherwise	1) Missing (due to Covid-19) at random: missing data not associated with outcome; 2) Missing (not due to Covid-19) not at random: Missing data indicates lack of response
	Sensitivity (Section 3.2.3.1.1)		Alternative handling of missing data	Missing data considered as no response	Missing not at random: Missing data indicates lack of response
	Sensitivity (Section 3.2.3.1.2)		Alternative handling of missing data	On-treatment missing data handled using multiple imputation	Missing at random: on-treatment missing data not associated with outcome
	Sensitivity (Section 3.2.3.1.3)		Alternative handling of missing data	Tipping-point analysis: post-treatment data considered missing for Intercurrent Event #3	Missing not at random: Assuming various treatment differences for missing data

Definition	Analysis Type	Estimand	Alternatives to main analysis	Missing data Handling	Missing data Assumption
	Sensitivity (for completers) ( Section 3.2.3.2 )	Modified primary estimand	Alternative analysis population	No imputation of missing data	Missing completely at random: completers are representatives of non-completers

All efficacy analyses based on ITT, unless otherwise specified.

- a Definition 1. Durable platelet response defined as a proportion of participants able to achieve platelet counts at or above 50,000/ $\mu$ L for  $\geq$ two-thirds of at least 8 non-missing weekly scheduled platelet measurements during the last 12 weeks of the 24-week blinded treatment period in the absence of rescue therapy, provided that at least 2 non-missing weekly scheduled platelet measurements are at or above 50,000/ $\mu$ L during the last 6 weeks of the 24-week blinded treatment period. Definition 1 not applicable to countries within the EU (EEA countries) and UK.
- b Definition 2. Durable platelet response defined as a proportion of participants able to achieve platelet counts at or above 50,000/ $\mu$ L for at least 8 out of the last 12 weeks of the 24-week blinded treatment period in the absence of rescue therapy. Definition 2 applicable to countries within the EU (EEA countries) and UK only.
- c Sensitivity analysis for mITT; sensitivity analysis for participants who did not receive Covid-19 vaccine during the last 16 weeks of double-blind treatment period. ([Section 3.2.3.2](#)).

### **3.2.3.1 Sensitivity Analysis – Primary estimand – Adults in ITT**

Each sensitivity analysis for durable response will be carried out via the same primary estimand and the same analysis method as defined in the main analytical approach ([Section 3.2.2](#)), using different handlings of missing data as specified below.

#### **3.2.3.1.1 Alternative assumption of missing data (missing data considered as no response) (for Definition 2)**

For durable platelet response Definition 2 ([Section 1.2.2.1](#)), missing weekly platelet count regardless of due to Covid-19 or not will be considered as no response assuming missing not at random.

#### **3.2.3.1.2 Alternative assumption of missing data (missing data handled via multiple imputation) (for Definition 2)**

As indicated in the primary estimand ([Section 3.2.2](#)), weekly platelet counts may not be available (due to missing or discontinuation) during the double-blind on-treatment period in participants who were not rescued (after 8 weeks of double-blind treatment and before Week 25) nor discontinued before Week 25 due to related AE or lack of response. These participants could be categorized into two groups: (1) those who discontinue IMP on or before Week 13 for which their missing data will not be imputed due to a large portion ( $\geq 50\%$ ) of missing data points during the double-blind treatment period) at participant level, and (2) those who stay on IMP beyond Week 13 for which their missing data will be imputed as specified below.

The missing data will be imputed using multiple imputation assuming missing at random and assuming logarithm transformed platelet values to be multivariate normally distributed. Specifically,

- Post-baseline missing weekly platelet counts (from Week 2 up to Week 25 during the double-blind on-treatment period) will be imputed using a model estimated from the participants who were not rescued (after 8 weeks of double-blind treatment and before Week 25) nor discontinued before Week 25 due to related AE or lack of response) and who stay on IMP beyond Week 13 and have available data during the double-blind on-treatment period at the corresponding visits.

Note: before multiple imputation, data will be set to missing for 4 weeks after the use of rescue therapy during the initial 8 weeks of double-blind treatment.

- The imputation model will include treatment group, randomization stratification factors, geographic region ([Section 3.1](#)) as classified variables and baseline value as a covariate.
- Binary durable platelet response will be derived from each of the imputed complete data and analyzed using the same analysis method as defined in the main analytical approach ([Section 3.2.2](#)). Statistical inference obtained from all imputed data will be combined using Rubin's rule (3).

The above sensitivity analysis via multiple imputation approach will be implemented under the following scenarios:

1. No missing data will need to be handled by multiple imputation in the placebo group (ie, missing data occurred in rilzabrutinib group only), OR
2. There are missing data that will need to be handled by multiple imputation in the placebo group and there are  $\geq 3$  participants in the placebo group who have completed the 24-week double-blind treatment without being rescued (after 8 weeks of double-blind treatment) and had post-baseline weekly platelet counts during the last 12 weeks of double-blind on-treatment period.

Please see sample SAS® code in [Section 5.7](#).

